---

**The following Amendment(s) have been made to this protocol since the date of preparation:**

Amendment No.	Date of Amendment	Local Amendment No:	Date of Local Amendment
----------------------	--------------------------	----------------------------	--------------------------------

---

---

---

---

---

---

## **NON-INTERVENTIONAL STUDY PROTOCOL SYNOPSIS**

---

### **Comparative, multicenter study estimating association between germline DNA-repair genes mutations and PD-L1 expression level in breast cancer**

---

#### **Co-ordinating Investigators of the Non-Interventional Study**

[name]  
[name]

[name]  
[name]

Study Site(s), number of subjects planned:

It is estimated that 240 patients will be entered into the study from 2 centers (Tatarstan Cancer Center and Republican State Clinical Oncological Dispensary in Ufa) in approximately 1 year.

Total planned Study period:

First subject in	January 2018
Last subject in	January 2019
Study Database lock	March 2019
Final Study Report	July 2019

#### **Medicinal Products (type, dose, mode of administration) and concomitant medication**

Not applicable. This is an observational study; therefore, patients are not assigned to a particular treatment by study protocol. Treatment will be according to current clinical practice.

## **Rationale for this Non-Interventional Study (NIS)**

Currently there is no precise data concerning the prevalence and types DNA-repair genes mutations, which lead to Homologous Recombination-deficiency, and its correlation with PD-L1 expression in BC.

## **Objectives of this Non-Interventional Study**

### Primary objective

To reveal association between the presence of germline DNA-repair genes mutations and PD-L1 expression level in tumour and immune cells in breast cancer (to reveal the differences of PD-L1 high tumor rate between patients with hereditary BC who have clinically significant germline mutations in DNA-repair genes (HR- deficiency) and patients with sporadic BC without such mutations).

### Secondary objectives

- To study the frequency of germline mutations forming the familial breast cancer in Tatarstan and Bashkortostan republics.
- To estimate the relation of the frequency of PD-L1 expression in tumour or/and immune cells with disease stage, receptor status (ER, PR, HER2neu), morphological type, Grade
- To estimate the relation of number of tumour-infiltrating lymphocytes (TILs) with disease stage, receptor status (ER, PR, HER2neu), morphological type, Grade and presence of clinically significant mutations in genes of DNA-repair system.

## **Study design**

This is a multicentre, non-interventional, prospective study to be carried out in representative oncology departments / institutions in order to determine the association between the presence of germline DNA-repair genes mutations and PD-L1 expression level in tumour and immune cells in breast cancer. No additional procedures besides those already used in the routine clinical practice will be applied to the patients. Treatment assignment will be done according to the current practice.

It is planned to enroll approximately 240 subjects in Russian Federation.

PD-L1 expression in tumor and immune cells in FFPE tumor tissue samples is the primary variable in this study.

Genetic testing of germline mutations in DNA-repair system genes (NGS) in blood samples receiving on Screening/ Baseline Visit and PD-L1 expression testing (IHC) in FFPE tumor tissue samples will be carried out in Republican Clinical Oncological Dispensary, Kazan.

The investigated group will consist of patients with clinical features of hereditary BC and revealed pathogenic germline mutations in DNA-repair genes (TP53 MLH1 MSH2 MSH6 PMS2 EPCAM APC MUTYH CDKN2A CDK4 ATM KIT PDGFRA CDH1 CTNNA1 PRSS1 SPINK1 BRCA1 BRCA2 FANCI FANCL PALB2 RAD51B RAD51C RAD54L RAD51D CHEK1 CHEK2 CDK12 BRIP1 PPP2R2A BARD1 PARP1 STK11 XRCC3). The control group will consist of patients with sporadic BC without mutations in these genes.

The PD-L1 expression level in tumor and immune cells and number of TILs in FFPE tissue samples received prior to start of any antitumor treatment will be estimated in both groups.

### **Target subject population**

Target study population will be women 18 years and older with BC diagnosed before enrolment into the study, consented to participate in this non-interventional study, who visit the oncology hospitals/departments in Kazan and Ufa.

### **Study variable(s):**

#### **Primary variable:**

PD-L1 expression in tumor and immune cells in FFPE tumor tissue samples estimated by ICH is the primary variable in this study. The primary variable value will be represented as “PD-L1 high” and “PD-L1 low”. PD-L1 expression for both TC and IC in the tumor microenvironment will be determined by the percentage of cells expressing PD-L1 at any intensity above background staining. PD-L1 will be defined as high if either  $\geq 25\%$  of TC or  $\geq 25\%$  of IC expressed PD-L1, and PD-L1 was defined as low if both  $< 25\%$  of TC and  $< 25\%$  of IC expressed PD-L1.

#### **Secondary variables:**

##### Patient characteristics:

- Age
- ethnicity
- Family oncological history with pointed localization of cancer (BC, OC, Prostate cancer, Pancreatic cancer or other localizations) and relation degree
- Individual oncological history: BC, OC, pancreatic cancer or other localizations

##### Disease information/ diagnostic procedures:

- Disease stage and TNM classification
- Morphological classification, Grade (1/2/3)

- Receptor status: ER, PR, HER2neu
- Extent of the disease
- Profile of germline mutations in DNA-repair system genes
- Number of TILs
- PD-L1 expression in tumor and immune cells in FFPE tumor tissue samples estimated by ICH as “PD-L1 high” or “PD-L1 low” based on 50% cut-off. PD-L1 will be defined as high if either  $\geq$  50% of TC or  $\geq$  50% of IC expressed PD-L1, and PD-L1 was defined as low if both  $<$  50% of TC and  $<$  50% of IC expressed PD-L1.
- 

## LIST OF ABBREVIATIONS AND DEFINITION OF TERMS

The following abbreviations and special terms are used in this NIS Protocol.

Abbreviation or special term	Explanation
AE	Adverse event
ADR	Adverse Drug Reaction
Assessment	An observation made on a variable involving a subjective judgement (assessment)
CRF	Case Report Form
LEC	Local Ethics Committee
PD-L1	Ligand of programmed depth receptor
GCP	Good Clinical Practice
NIS	Non-Interventional Study
NISA	Non-Interventional Study Agreement
NISP	Non-Interventional Study Protocol
NISR	Non-Interventional Study Report
BC	Breast Cancer
OC	Ovarian Cancer
PI	Principal Investigator responsible for the conduct of a NIS at a site
PRO	Patient Reported Outcomes
PS	Performance Status
Variable	A characteristic of a property of a subject that may vary eg, from time to time or between subjects
WHO	World Health Organization
TILs	Number of tumor-infiltrating lymphocytes
IHC	Immunohistochemistry
NGS	Next generation sequencing
ER	Estrogen receptor
PR	Progesterone receptor

## 1. INTRODUCTION

### 1.1 Background

Breast cancer (BC) occupies the first place among malignancy in females (29.9% of all tumors in female patients in Russian Federation in 2015) [1].

One of the most perspective direction of the oncotherapy is anticancer immunotherapy – employment of inhibitors of immune checkpoints. Immune checkpoints inhibitors (such as anti-PD-1 and anti-PD-L1 antibodies) have shown good clinical efficiency in clinical research to cure such malignant tumor with high mutation load, as melanoma, lung cancer, and others.

One of the hypothesis of such effect states that, usually, more cancer neoantigens are synthetized in the tumors with high mutation load (driven by genome instability), causing severe lymphoid infiltration [2-3]. This situation is balanced by overexpression of such inhibitors of the immune response as PD-1 and PD-L1 [4 - 6].

Breast cancer – is relatively heterogenic tumor, with different genetic, morphological and phenotypic forms.

Despite relatively low expression of PD-L1 in BC in general, there are reasons to believe that genetic instability, driven by mutations in genes involved in DNA repair, can increase the immunogenicity and, thus, the expression of PD-L1 in BC.

To date, it is widely accepted that 5-10% of BC cases are represented by hereditary types, i.e. mediated by germline pathogenic mutations in genes of DNA reparation pathways. Hereditary breast cancer (HBC), as well as ovarian cancer (OC), caused by mutations in genes BRCA1, BRCA2, CHEK2, TP53 и PTEN, and others. Thus, one of the promising directions here is to understand the inter-relation among germline pathogenic mutations associated with HBC, and activity of PD-L1. It would allow to optimize selection of anti-PD-L1 therapy, by forming group of patients (matching criteria of HBC) with high level of PD-L1 expression in cancer cells and tumor-infiltrating lymphocytes.

### 1.2 Rationale for the proposed study:

It is important to mention, that nearly all information, accumulated on the HBC and OC in Russia is based on the analysis of the females of Slavic origin [7-8]. There are reasons to assume that representatives of other ethnic groups (total number of nationalities in Russian Federation exceeds 100) in Russia, have different from Slavs spectrum of founder-mutations in BRCA1/2 genes. Thus, generally accepted diagnostic procedures aimed on the detection of the most frequent in Slavs founder-mutations should result in high number of false-positive results [7].

For example, in the pool of patients with BC in Bashkortostan republic, mutation 5382insC BRCA1 are found in less than 4% of cases [11]. Among, patients in Sakha republic (Yakutia), typical for West and East European (Slavs) populations mutations 5382insC, 4153delA, C61G in BRCA1 was not detected at all. Such kind of discrepancy, suggests the domination of East-Eurasian component and low number of West-European lines of mtDNA and Y-chromosomes in the population of eastern regions of Russia [10, 12].

Also, currently there are no comprehensive studies in Russia on the frequencies of mutations in other than BRCA1/2 genes involved in DNA reparation.

Here we propose complex and comprehensive research program aimed to detect relation among presence of germline pathogenic mutations in the DNA repair network genes (including BRCA1/2) and frequency of high PD-L1 expression in cancer cells and tumor-infiltrating lymphocytes in BC.

Understanding of inter-relation of presence of germline pathogenic mutations in BC and expression of PD-L1 can become one of the important approaches to identify group of patients, responsive to therapy by inhibitors of immune checkpoints or to combined therapy by target (PARP inhibitors) and immunotherapeutic drugs.

## **2. NIS OBJECTIVES**

### **2.1 Primary objective**

To reveal association between the presence of germline DNA-repair genes mutations and PD-L1 expression level in tumour and immune cells in breast cancer (to reveal the difference of PD-L1 high tumor rate between patients with hereditary BC who have clinically significant germline mutations in DNA-repair genes (HR- deficiency) and patients with sporadic BC without such mutations).

### **2.2 Secondary objectives**

- To study the frequency of germline mutations forming the familial breast cancer in Tatarstan and Bashkortostan republics.
- To estimate the relation of the frequency of PD-L1 expression in tumor or/and immune cells with disease stage, receptor status (ER, PR, HER2neu), morphological type, Grade
- To estimate the relation of number of tumor-infiltrating lymphocytes (TILs) with disease stage, receptor status (ER, PR, HER2neu), morphological type, Grade and presence of clinically significant mutations in genes of DNA-repair system.

## **3. STUDY PLAN AND PROCEDURES**

### **3.1 Overall study design and flow chart**

This is a multicentre, non-interventional, prospective study to be carried out in representative oncology departments / institutions in order to determine the interrelation between the presence of germline DNA-repair genes mutations and PD-L1 expression level in tumour and immune cells in breast cancer. No additional procedures besides those already used in the routine clinical practice will be applied to the patients. Treatment assignment will be done according to the current practice.

It is planned to enroll approximately 240 subjects in 2 centers (Tatarstan Cancer Centre and Republican Clinical Oncological Dispensary Ufa).

PD-L1 expression in tumor and immune cells in FFPE tumor tissue samples estimated by IHC is the primary variable in this study. The primary variable value will be represented as “PD-L1 high” and “PD-L1 low”.

Genetic testing of germline mutations in DNA-repair system genes (NGS) in blood samples receiving on Screening/ Baseline Visit and PD-L1 expression testing (IHC) in FFPE tumor tissue samples will be carried out in Tatarstan Cancer Centre, Kazan.

The PD-L1 expression level in tumor and immune cells and number of TILs in FFPE tissue samples received prior to start of any antitumor treatment will be estimated in both groups.

The only one visit is planned for all patients in this study.

Information regarding patient demographics, the disease characteristics, and diagnostic tests results will be taken from the medical records.

Information about familial and individual oncological history will be received on the visit.

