#### Material and methods:

IHC testing of PD-L1 expression level in tumor tissue samples will be conducted using VENTANA PD-L1 (SP263) Rabbit Monoclonal Primary Antibody. PD-L1 expression for both TC and IC in the tumor microenvironment will be determined by the percentage of cells expressing PD-L1 at any intensity above background staining. PD-L1 will be defined as high if either  $\geq 25\%$  of TC or  $\geq 25\%$  of IC expressed PD-L1, and PD-L1 was defined as low if both,  $<25\%$  of TC and,  $<25\%$  of IC expressed PD-L1.

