### Study Flow Chart

**Table 1** **Study Plan**

Study procedures	Screening/ Baseline Visit (day 0)	Biomarker analysis	
		Detection of presence/absence of germline mutations in DNA- repair system genes (NGS)  (1-3 months after day 0)	Estimation of PD-L1 expression level and TILs (IHC)  (1 month after NGS results)
Informed consent	X		
Patient demographics	X		
Medical history	X		
Inclusion / Exclusion criteria	X		
Receiving of blood samples for NGS	X		
Genetic testing		X	
Request of FFPE tumor tissue samples for IHC	X		
IHC			X
Disease information	X		

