## **12. DATA MANAGEMENT**

### **12.1 Collection, monitoring, processing of data and archiving**

Each enrolled patient would be assigned with unique identification number (the least available from the pre-designed sequence). The individual Case Report Form (CRF), specially designed for this study, will be completed for each patient enrolled.

The collection of data from out-patient medical records or disease histories for hospitalised patient, as well as collection of data received by a physician during the routine patient examination will be performed. Any special data collection procedures are not stipulated within the framework of this study. All patient data will be recorded by the participating physician both in the source documents and in the CRF. Source documents are kept by physician.

Signed Informed Consents will be kept by the physician during the study and after the study completion.

Database will have to be completed, and then passed appropriate quality check, considered to be full and accurate, and then will be locked. Collected data will be analyzed.

Essential study documents must be retained by the participating physician for as long as needed to comply with local and international regulations. No source documents, containing patients' personal data, should be taken away from the physician.

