## **13. STATISTICAL METHODS AND SAMPLE SIZE DETERMINATION**

### **13.1 Statistical evaluation – general aspects**

This is prospective non-interventional study designed as a case-control type for exact assessment of influence of the mutations in DNA repair genes presence on PD-L1 expression in BC. Case-control studies are often used for comparison of influence a predictive factor on a outcome. The primary variable (PD-L1 expression) and explored risk factor (mutations in DNA repair genes presence) will have nominal value: high/low and yes/no respectively.

A Non-Interventional Study is a study in which epidemiological methods including other methods that can be used to analyse human population health data.

All statistical analyses will be performed by means of the statistical software system.

A comprehensive Statistical Analysis Plan will be prepared before database lock.

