### **13.3 Description of analysis sets**

All Enrolled set will consist of all the subjects who signed informed consent to enter the study. Patient disposition and baseline characteristics and demography as well as analysis of the primary and secondary objectives will be based on the set.

All patients will be enrolled in 2 groups 1:1. The analyses of primary objective will be conducted based on the results in these groups:

- The investigated group will be consists of patients with clinical features of hereditary BC (according to NCCN breast and/or ovarian cancer genetic assessment guidelines V1.2017) and revealed clinically significant (pathogenic) germline mutations in DNA-repair genes (TP53 MLH1 MSH2 MSH6 PMS2 EPCAM APC MUTYH CDKN2A CDK4 ATM KIT PDGFRA CDH1 CTNNA1 PRSS1 SPINK1 BRCA1 BRCA2 FANCI FANCL PALB2 RAD51B RAD51C RAD54L RAD51D CHEK1 CHEK2 CDK12 BRIP1 PPP2R2A BARD1 PARP1 STK11 XRCC3) regardless morphological type, grade, receptor status and extent of the disease.

- The control group will be consisting of patients with sporadic BC without germline mutations in DNA-repair genes (TP53 MLH1 MSH2 MSH6 PMS2 EPCAM APC MUTYH CDKN2A CDK4 ATM KIT PDGFRA CDH1 CTNNA1 PRSS1 SPINK1 BRCA1 BRCA2 FANCI FANCL PALB2 RAD51B RAD51C RAD54L RAD51D CHEK1 CHEK2 CDK12 BRIP1 PPP2R2A BARD1 PARP1 STK11 XRCC3) regardless morphological type, grade, receptor status and extent of the disease.

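### PD-L1 and TILs are read one month after the sequencing result that helps define the groups, and no section masks the reader to that result or to group: an avoidable risk, not a demonstrated bias

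*Combined protocol and SAP*

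**What the plan says.** - **Place.** Section 3.1 assigns blood sequencing to the Kazan centre "and PD-L1 expression testing (IHC) in FFPE tumor tissue samples will be carried out in Tatarstan Cancer Centre, Kazan". The synopsis says the same under a different name for the Kazan institution. Neither names a site for TILs. Table 1 lists them in the same IHC column as PD-L1, so Kazan is an inference for TILs.
- **Order.** Table 1 places sequencing 1 to 3 months after day 0, and the PD-L1 and TIL reading "1 month after NGS results".
- **Groups.** Under section 13.3 the investigated group has hereditary features "and revealed clinically significant (pathogenic) germline mutations in DNA-repair genes". Controls have sporadic disease and no mutation in the same genes.
- **Primary outcome.** Under Material and methods, PD-L1 in tumour and immune cells is "determined by the percentage of cells expressing PD-L1 at any intensity above background staining". A tumour is high if either compartment reaches 25%. Section 8.2 adds a secondary classification at 50%.
- **Direction.** Section 1.1 argues that genetic instability from repair-gene mutations "can increase the immunogenicity and, thus, the expression of PD-L1 in BC".
- **Identifiers and records.** Section 12.1: "Each enrolled patient would be assigned with unique identification number (the least available from the pre-designed sequence". Also: "All patient data will be recorded by the participating physician both in the source documents and in the CRF".
- **Analysis plan.** Section 13.1: "A comprehensive Statistical Analysis Plan will be prepared before database lock".
- **Masking.** The design, IHC, variable, monitoring and data-management sections do not mention masking, coded slides or what the reader may know.

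**The concern.** Carrier status exists at the centre that does the PD-L1 staining before any slide is scored. The score needs judgement about background staining and about a percentage, and either of two compartments can carry a tumour over the 25% line. A reader who knew the group and the hypothesis could resolve borderline slides in the expected direction without intending to.

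At stake are the primary odds ratio and the secondary comparison of TILs by mutation status. The logistic regression in section 13.4 sees only the recorded high or low call. It cannot tell a reading shift that follows group from a true association.

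**Working it through.** **Check of the plan's own figure.** Section 14, third scenario, uses P0 = 0.14, P1 = 0.30, two-sided α = 0.05 and β = 0.2. With pooled P = 0.22:

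- A = 1.960 × √(0.22 × 0.78 × 4) = 1.624
- B = 0.842 × √(2 × 0.30 × 0.70 + 2 × 0.14 × 0.86) = 0.684
- N = (A + B)² / 0.16² = 208.1, against 208 stated
- Continuity correction 1/(0.5 × 0.16) = 12.5 per group, so 104.1 + 12.5 = 116.6, or 117 per group and 234 in total, as stated

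The plan rounds this to about 120 per group. Masking changes none of these figures.

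**Illustration of what masking protects.** The documents give no reader-error rate and no share of tumours near 25%, so the error rates below are assumptions.

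- n = 120 per group and a true high rate of 14% in both groups, so there is no true difference
- u = share of truly low carrier tumours scored high, with no errors in controls and none downward; this is the least favourable pattern
- Truly low carrier tumours: 120 × 0.86 = 103.2
- Observed carrier rate: p1 = 0.14 + 0.86 × u
- OR = [p1/(1 − p1)] / [0.14/0.86]
- False-positive rate: exact binomial enumeration of a two-sided 5% test

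| u | tumours upgraded | p1 | OR | Pearson | Wald (logistic) |
|---|---|---|---|---|---|
| 0 | 0 | 0.1400 | 1.00 | 5.0% | 4.7% |
| 1% | 1.0 | 0.1486 | 1.07 | 5.5% | 5.1% |
| 2% | 2.1 | 0.1572 | 1.15 | 6.7% | 6.2% |
| 5% | 5.2 | 0.1830 | 1.38 | 15.0% | 14.1% |

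Example for u = 5%: p1 = 0.14 + 0.043 = 0.183, and OR = (0.183/0.817)/(0.14/0.86) = 1.38.

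**Same error rate from a masked reader.** If 2% or 5% of low tumours are upgraded in both groups, both rates are 0.1572 or 0.183. The OR is 1.00 and the Pearson false-positive rate is 5.1% in each case. The harm comes from error that follows group, not from error as such.

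**The case against.** **The argument is from silence.** One institution is not one person, and nothing says that sequencing results pass to whoever reads the slides. This stands. A reader might infer from the shared site and the timing that the pathologist knows carrier status, or that the order of tests is itself a fault. The documents support neither. They fail to prevent access; they do not describe it.

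**The 50% classification is already a check.** In part it is. If shifts were confined to scores near 25%, the 50% call would not move, and a disagreement between the two cut-offs could give a warning. It does not cover TILs, and it would not expose a shift across the whole scale.

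**The 15.0% depends on a severe scenario.** This also stands. The 5% applies to all truly low carrier tumours. If, as an assumption, 5%, 10% or 20% of them lie near the cut-off, the reader would have to upgrade 100%, 50% or 25% of those. Section 1.1 itself describes PD-L1 expression in breast cancer as relatively low in general, which makes a large borderline share less plausible.

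**The analysis plan may deal with it.** It may be tempting to say that it will come too late. Section 13.1 sets only a latest date, so the plan could precede the readings. But it need not, so it cannot be relied on to set masking in time.

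**The patient number already masks.** Only if the reader cannot look up sequencing results filed under the same number. Section 12.1 does not say so.

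Some front pages are absent from the public text and cannot be checked. The sections where masking would belong are present and silent.

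**Conclusion.** The concern holds as a gap in procedure for the primary comparison. PD-L1 is read at the Kazan centre after the sequencing result exists there, on a percentage scale with a cut-off, under a directional hypothesis, and no stated rule keeps the result or group from the reader. The same applies to TILs if, as Table 1 suggests, they are read in the same step.

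Bias is not demonstrated, and its size cannot be estimated from the documents. Under the stated assumptions (14% high, 120 per group, errors only upward and only in carriers), 1% to 2% upgrading has a small effect: OR 1.07 to 1.15 and a false-positive rate of 5.5% to 6.7%. At 5%, about five tumours in 103, the OR is 1.38 and the rate 15.0%. A reader might take 15.0% as the expected error rate of the study; it is only the outcome of one unfavourable assumption. The change is worth making because it is cheap and the planned regression cannot repair the problem afterwards. Confidence is medium, because masking may already be the laboratory's practice.

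**What to change.** Keep the order of sequencing and then IHC. State in section 3.1 and under Material and methods that:

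1. Slides for PD-L1 and TILs are read under a code that does not appear on the sequencing report, or under the study number with the reader having no access to sequencing results.
2. The person scoring PD-L1 and TILs is not given the sequencing result, the group, or the family and personal cancer history that Attachment 3 uses to define hereditary features. Withholding receptor status as well goes beyond what is needed.
3. Scores are recorded and fixed before they are linked to sequencing data.

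The cost is slide coding, access control and a change in the order of CRF entry, because section 12.1 now has the participating physician record all patient data in one form per patient. No extra patient or procedure is needed. No extra reader is needed either, provided the existing reader does not already know the patient's mutation status or group. The documents do not identify that person, so the sponsor should confirm this first.
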